# **13.1** Screening Examination

The screening examination will take place between Day -21 and -1. An informed consent must be signed by the patient before any study specific screening procedures take place. Information collected prior to the signing of informed consent according to standard of care for procedures such as KPS, labs, history and physical, and MRI, etc. may be used to determine eligibility. Subject data to be collected at the Screening Examination is listed in the table above and includes physical and neurological examination; vital signs and weight; ECG, laboratory studies (complete blood count with differential, complete metabolic panel, PT/aPTT, and beta-HCG); past medical history; and concomitant medications (including but not limited to steroids and anticonvulsants). Additional

baseline testing will be completed for the following: cognitive testing, HRQoL Measurements, and hair loss evaluation.

The screening MRI or CT scan will be uploaded to the Duke central core for final review of eligibility. This will be required for all subjects. The clinical centers will be notified of the final determination of eligibility prior to the subject completing any study visit.

The pathology report used to determine eligibility, which includes any tumor markers will be redacted and uploaded to the sponsor electronic data capture system.

If a subject is found to be ineligible to participate in the study, the patient will not be randomized to a treatment arm and minimal records regarding the subject and the reason for screen failure will be retained.

## 13.2 Run-In Period

Not applicable.

## **13.3** Chemoradiation Treatment Period (with and without BMX-001)

The treatment period for BMX-001 is eight weeks. This consists of treatment prior to start of chemotherapy- RT, during the six weeks of concurrent daily TMZ and standard RT with BMX-001 (Phase 1 and Phase 2 (Arm A)) followed by 2 weeks of BMX-001 (Phase 1 and Phase 2 (Arm A)). For subjects in Arm B, this period is six weeks of concurrent daily TMZ with standard RT followed by 2 weeks of no treatment. For subjects in Arm B, they do not need to return to the clinical center for a study visit once TMZ and RT is complete for visits at Week 7 and Week 8.

# 13.4 BMX-001 Treatment Criteria

If adverse events occur that require holding BMX-001, the dose will remain the same once treatment resumes. Missed doses should be made up at the end of treatment to achieve the total number of planned doses (17).

#### 13.4.1 Phase 2 - Criteria for holding BMX-001

#### Non-Hematologic Criteria

- The occurrence of non-hematologic grade 3 or greater adverse events considered to be possibly, probably, or definitely related to BMX-001 during treatment with BMX-001, excluding grade ≥ 3 alopecia and elevation in alkaline phosphatase, grade ≥ 3 nausea or vomiting unless occurring despite the use of standard anti-emetics; and grade ≥ 3 hypertriglyceridemia or hypercholesterolemia unless occurring despite standard lipid lowering agents.
- 2. Intolerable  $\geq$  Grade 2 Injection Site Reactions
- 3.  $\geq$  Grade 2 electrocardiogram prolonged QTc interval

#### Hematologic Criteria

- 1. Grade 4 neutropenia (ANC, including bands,  $\leq$  500 cells /µl);
- 2. Grade 3 thrombocytopenia (platelet count of  $\leq$  50,000 cells/µl);

#### 13.4.2 Phase 2- Re-treatment Criteria for BMX-001

Non-Hematologic

- 1. Resolution of any grade 3 or greater toxicity felt to be possibly, probably or definitely attributable to BMX-001 to grade 1 or pre-treatment baseline.
- 2. Resolution of Intolerable  $\geq$  Grade 2 Injection Site Reactions to  $\leq$  Grade 1
- 3. Resolution of Grade 2 electrocardiogram prolonged QTc interval to baseline, or after review by sponsor.

#### Hematologic

- 1. ANC  $\geq$  1,000 cells/µl
- 2. Platelets  $\geq$  50,000 cells/µl

#### 13.4.3 Phase 2- Discontinuation Criteria for BMX-001

Inability to resolve any grade 3 or greater toxicity felt to be possibly, probably or definitely attributable to BMX-001 to grade 1 or pre-treatment baseline within 21 days.

For both non-hematologic and hematologic events, if any event requires holding BMX-001 > 21 days without retreatment, BMX-001 would not be started again. In these cases, subjects should continue to be followed for survival without the completion of study treatment visits.

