### 9.1.5 Missed Doses

Regardless of the reason for withholding study drug treatment, the maximum allowable length of treatment interruption is 3 weeks. If BMX-001 is withheld for greater than 3 weeks, BMX-001 will be discontinued. If BMX-001 is discontinued for missed doses, the patient will remain on the study and all planned study endpoints will be assessed. Any missed doses should be made up at the end of treatment, so that the subjects complete the planned number of doses (which is 17). Any missed doses of BMX-001 should be documented with the reason included.

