#### 13.7.2 Follow-up Requirements for Early Withdrawal

Subjects who are withdrawn due to toxicity or progressive disease will be followed for as long as they are receiving treatment for their HGG at the clinical center. Study visits will cease, however data collection for survival should continue at a minimum of three month intervals. For subjects who voluntarily withdraw, there is not an end of study visit, unless deemed appropriate by the PI. Early withdrawal subjects will be followed for survival where possible, except for subjects that specifically request not to have any further follow up.

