12.1 ENDPOINT

Progression-Free Survival (PFS) is defined as the time between initiation of protocol treatment and disease progression or death. If the patient remains alive without disease progression, then PFS will be censored at last follow-up. Analyses similar to those described for OS will be generated for PFS.

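### Protocol 9.1.5 and 13.4.3 set different follow-up after a BMX-001 hold of more than 3 weeks; only Arm A can meet that trigger, and PFS is the endpoint most exposed

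*Protocol*

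**What the plan says.** Four places bear on this.

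- **Protocol 9.1.5 (Missed Doses)** sets one limit for all causes: "Regardless of the reason for withholding study drug treatment, the maximum allowable length of treatment interruption is 3 weeks". Beyond that limit BMX-001 is discontinued. It then adds: "If BMX-001 is discontinued for missed doses, the patient will remain on the study and all planned study endpoints will be assessed".
- **Protocol 13.4.3 (Discontinuation Criteria)** covers hematologic and non-hematologic events: "if any event requires holding BMX-001 > 21 days without retreatment, BMX-001 would not be started again". Its follow-up rule is: "In these cases, subjects should continue to be followed for survival without the completion of study treatment visits".
- **Protocol 13.5 and 13.7.2** deal with patients who come off study. Section 13.5 lists unacceptable toxicity and TMZ allergy, which can occur in either arm, and BMX-001 allergy, which can occur only in Arm A. Section 13.7.2 begins: "Subjects who are withdrawn due to toxicity or progressive disease will be followed for as long as they are receiving treatment for their HGG". For these patients, "Study visits will cease, however data collection for survival should continue at a minimum of three month intervals".
- **SAP 12.1** says of PFS: "If the patient remains alive without disease progression, then PFS will be censored at last follow-up". SAP 12.2 analyses PFS in all patients by assigned arm. Neither section defines last follow-up or gives a rule for missed progression assessments.

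**The concern.** Take an Arm A patient whose adverse event has kept BMX-001 on hold past the limit. One site can cite 9.1.5 and carry on with imaging, cognition, blood counts and adverse-event assessment. Another can cite 13.4.3 and record survival only. Both would be following the protocol.

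Arm B has no BMX-001 to hold, so this route out of assessment exists on one side of the randomisation only, and it is tied to toxicity. In an open-label trial with an intent-to-treat PFS comparison, a data-collection rule of that kind can make the arms differ in how completely progression is observed, apart from any treatment effect.

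**Working it through.** **1. Is it the same event?** The two sections side by side:

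| | Protocol 9.1.5 | Protocol 13.4.3 |
|---|---|---|
| Limit on the hold | more than 3 weeks | more than 21 days (3 × 7 = 21) |
| Cause | any reason | any hematologic or non-hematologic event |
| BMX-001 | discontinued | not restarted |
| Follow-up | on study, all planned endpoints | survival, without study treatment visits |

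The first three rows coincide for an event-driven hold; the last does not.

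**2. Who can meet the trigger?** Only Arm A. The hematologic hold criteria in Protocol 13.4.1 (grade 4 neutropenia, grade 3 thrombocytopenia) require no attribution to BMX-001. A prolonged cytopenia of the kind TMZ causes could therefore bring an Arm A patient under 13.4.3. In Arm B the same event falls under Protocol 11.4, which governs TMZ dosing and changes no follow-up.

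**3. What is lost under each reading of 13.4.3?**

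- *Wide reading (survival only):* MRI, cognition, blood counts and adverse-event assessment all end.
- *Narrow reading (treatment-period visits only):* the remaining visits to week 8 are dropped. Table 4 schedules weekly blood counts in weeks 2–8 and ongoing toxicity assessment. The thrombocytopenia and adverse-event endpoints run to 2 weeks after radiation (Protocol 16.5.2.2 and 16.5.2.3). Section 9.1.5 would keep these data. One qualification: Arm B has no research visits at weeks 7 and 8 (Protocol 13.3), so on this reading the imbalance lies mainly in the visits before then.

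**4. PFS.** Take a patient alive with no recorded progression, last assessed for progression at time *a* and last contacted for survival at a later time *c*.

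- If last follow-up means *a*, the patient is censored early. If patients who stop for toxicity differ in progression risk, the censoring is informative, in an unknown direction.
- If it means *c*, the patient counts as progression-free from *a* to *c* although nobody looked. Missed progressions would lengthen Arm A PFS.
- If the patient dies, the death is a PFS event either way. Any unseen earlier progression means that event is dated too late.

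SAP 12.1 allows either of the first two, so the sign of the bias cannot be read from the plan.

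**5. OS.** Survival follow-up continues under both sections, so the primary analysis at 84 deaths is untouched.

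**6. Cognition.** Inputs from SAP 9.4.2 are 52 Arm A and 42 Arm B patients with week-24 pairs, SD 30, two-sided 0.05 and 80% power. The normal approximation gives (1.960 + 0.842) × 30 × √(1/52 + 1/42) = 17.44. The noncentral t gives 17.62, which reproduces the SAP's 17.6.

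Completeness among patients who received protocol treatment (78 and 71, SAP 10.3.2):

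- Arm A: 52/78 = 66.7%, so 26/78 = 33.3% missing.
- Arm B: 42/71 = 59.2%, so 29/71 = 40.8% missing.
- Chi-square p = 0.34.

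Both arms lose data, Arm B somewhat more.

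**7. Size.** The documents give no Phase 2 rate of stopping after a hold over 21 days. Assume 0–20% of 78 and, as an extreme case, that all such patients lack week-24 data solely because of 13.4.3 and could be recovered:

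| Assumed rate | Patients | Arm A n | Detectable difference | Power at 17.6 |
|---|---|---|---|---|
| 0% | 0 | 52 | 17.62 | 79.9% |
| 5% | 3.9 | 55.9 | 17.34 | 81.2% |
| 10% | 7.8 | 59.8 | 17.09 | 82.3% |
| 20% | 15.6 | 67.6 | 16.66 | 84.1% |

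The power effect is small. What matters is possible bias, chiefly in PFS. The documents give no PFS loss by arm, so that part cannot be computed.

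**The case against.** The strongest defence is that 13.4.3 drops only dosing-period visits. Protocol 13.3 describes BMX-001 treatment as an eight-week period, and Table 4 shows the adjuvant phase separately. Table 4 footnote v continues adjuvant visits until MRI progression even if adjuvant TMZ stops. Protocol 13.8.4 ties MRI to standard-of-care visits. SAP 8 says patients go on being followed for progression. This stands to the extent that 13.4.3 is ambiguous: it does not expressly end imaging or cognitive testing. It does not remove the conflict, because even the narrow reading drops blood-count and toxicity visits that 9.1.5 keeps.

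Section 9.1.5 can also be confined to stops for missed doses, leaving adverse events to 13.4.3. Its opening words on cause work against that reading.

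The SAP already has some protection. Section 9.1 compares cognitive drop-out by arm, section 9.3 adds a pattern-mixture model, and section 7 lists withdrawals by arm with reasons. These help with cognition. They do not settle PFS censoring, and a patient moved to survival-only follow-up without formal withdrawal may not appear in the section 7 list.

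Finally, the SAP describes dosing in the past tense, so amending the protocol recovers no missed visit. That is right, and it shifts the weight of the remedy to the SAP wording and to retrieving routine MRI dates.

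**Conclusion.** The protocol contradicts itself on follow-up after a BMX-001 hold of more than 3 weeks, and the passages must be reconciled. The 13.4.3 trigger, and the BMX-001 allergy exit in 13.5, exist only in Arm A. PFS is the main exposure, with unknown direction; platelet and adverse-event data are also exposed; cognition is secondary; OS is not affected. The number of patients is not documented: 5–10% of 78 would be about 4 to 8, but that rate is an assumption.

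Three stronger readings are tempting and are not supported:

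- *That 13.7.2 confirms a survival-only rule for anyone stopping BMX-001.* It covers patients withdrawn from the study, for toxicity or progression, in either arm.
- *That cognition demonstrably loses data in Arm A alone.* The SAP's counts show more missing in Arm B, although without reasons by arm they cannot exclude toxicity-related loss in Arm A. The main cognition analysis is in treated patients, and SAP 6 requires at least 6 weeks or 13 doses of BMX-001. Some early stoppers leave that analysis whatever the visit rule, although the SAP 19 table also lists cognition for ITT.
- *That affected patients are censored for PFS at their last study visit.* SAP 12.1 does not say so.

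**What to change.** 1. Reconcile Protocol 13.4.3 with 9.1.5 so that stopping BMX-001 does not by itself end scheduled endpoint assessments (MRI and progression, cognition, blood counts, adverse events).
2. Clarify that 13.5 and 13.7.2 apply only to patients withdrawn from the study.
3. In SAP 12.1, state that PFS is not censored at BMX-001 discontinuation, and that patients without an event are censored at their last progression assessment. Deaths remain events under the existing definition.
4. For patients already affected, use standard-of-care MRI dates to establish progression status.
5. Report by arm how many patients had assessments stopped early.

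The cost is a protocol clarification, a few lines in the SAP, and retrieval of routine scan dates for what is probably a small number of patients. Items 3 to 5 can still help with treatment complete, and should be settled before PFS is analysed. No dosing, holding or discontinuation rule needs to change.

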## 13.5 End of Study

The end of study for a subject will occur when the subject comes off study for the following reasons: completion of all study tests/procedures, progressive disease, unacceptable toxicity, allergic reaction to TMZ, allergic reactions to BMX-001, non-compliance with study follow-up, or withdrawal of consent. Patient death due to progressive disease will not be reported as a SAE. It is the intent that all patients will be followed as long as possible for survival. See Section 13.7.2 for follow-up requirements after the patient comes off study.

## 13.6 Overall Study Completion

The study will be considered complete once enrollment has been met, follow-up procedures on all subjects have been conducted, and data analysis is concluded. The study may also be terminated early for any reason by the sponsor. In order to terminate the study with the external IRB, all data extraction and analysis must be complete. Therefore, if any articles for publication are derived from the current study, they must be submitted and accepted with no further need for additional data review prior to termination with the IRB.

Subjects that are lost to follow-up will be documented in the patient record and in the database.

## **13.7** Withdrawal of Subject(s)

#### 13.7.1 Criteria for Early Withdrawal

Subjects may voluntarily withdraw from the study at any time. The PI may also withdraw a subject from the study at any time based on his/her discretion. Reasons for PI-initiated withdrawal may include, but is not limited to the following:

- Adverse events
- Abnormal laboratory values
- Abnormal test procedure results
- Protocol deviation
- Administrative issues
- Disease progression- Patients will still complete cognitive testing (HVLT-R, COWA, TMT, BAC App) after coming off for disease progression. All other assessments will stop at the point of

progression. If a patient came off study for disease progression prior to this protocol amendment, and is still having study visits or is within 3 months from their 12 month visit, they should be contacted and asked to complete the cognitive testing at their next visit.

Pregnancy

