h DTI/Susceptibility Imaging is for clinical centers selected by the sponsor and completed at baseline, during the Adjuvant Phase before the start of the first cycle of adjuvant temozolomide, as well as 6 months (approximately 24 weeks, +/- 2 weeks) after radiotherapy/chemotherapy

i Toxicity assessment will continue to be obtained at every SOC clinic visit during the Adjuvant Phase for a minimum of 30 days after last BMX-001 treatment for subjects receiving BMX-001 or last chemo/RT for subjects not receiving BMX-001, and also followed for any unresolved adverse events considered related to study therapy.

j For BMX-001, this dose will be the loading dose. In Phase 2- Applicable only for patients in Arm A.

k For BMX-001, doses (50% of the loading dose) will be twice a week subcutaneously weeks 1-8. There will only be two doses per week regardless of being a loading or maintenance dose. In Phase 2- Applicable only for patients in Arm A. I For patients in Phase 2 Arm B (standard RT + TMZ without BMX-001), vital sign evaluation will only be required on days of the History and Physical assessment.

m Arm A: Patients will be monitored at drug administration with vital signs and injection site reaction at pre dose, at 5 (+/-2), 15 (+/-3), 30 (+/-5), and 60 (+/-5) minutes post administration on the BMX-001 loading dose. Patients will be monitored at drug administration with vital signs and injection site reaction at pre dose, at 5 (+/-2), 15 (+/-3) and 30 (+/-5) minutes post administration on BMX-001 maintenance injection days. See Section 0.

o Phase 2 only, subjects will be randomized after all eligibility criteria is confirmed.

p For Phase 2: For subjects in Arm A, this column is the day of the BMX-001 Loading Dose. For Subjects in Arm B, these items should occur -5 to 0 days prior to the start of RT. The procedures for this visit should not take place until final eligibility is confirmed and randomization has occurred.

q In Phase 2, subjects randomized to Arm B will NOT have a Week 7 or Week 8 research study visit.

r In Phase 2, subjects randomized to Arm B do not have a Week 1 study visit, although they will be in the clinic for the start of RT and TMZ.

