# 14.1 Adverse Events

An adverse event (AE) is any untoward medical occurrence in a study subject which does not necessarily have a causal relationship with this treatment. For this protocol, the definition of AE also includes worsening of any pre-existing medical condition. An AE can therefore be any unfavorable and unintended or worsening sign (including an abnormal laboratory finding), symptom, or disease that occurs in any subject enrolled in this clinical trial. It may or may not be related to use of the BMX-001. Abnormal laboratory findings without clinical significance (based on the Principal Investigator's judgment) should not be recorded as AEs. But laboratory value changes that require therapy or adjustment in prior therapy are considered adverse events.

From the time the subject signs the informed consent form through 30 days after completion of the final BMX-001 treatment (for subjects in Arm A, this will be 30 days after the last chemo/RT for subjects in Arm B), all AEs must be recorded in the subject medical record and adverse events case report form.

AEs will be assessed according to the CTCAE version 4.03. If CTCAE grading does not exist for an AE, the severity of the AE will be graded as mild (1), moderate (2), severe (3), life-threatening (4), or fatal (5).

Attribution of AEs will be indicated as follows:

- Definite: The AE is clearly related to the BMX-001
- Probably: The AE is likely related to the BMX-001
- Possible: The AE may be related to the BMX-001
- Unlikely: The AE is doubtfully related to the BMX-001
- Unrelated: The AE is clearly NOT related to the BMX-001

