11.1 ENDPOINTS

The phase 2 portion of this study has two adverse event endpoints:

(1) The proportion of patients who experience any grade 3 or 4 adverse event during radiation and temozolomide treatment, and

(2) The proportion of patients who experience a grade 3 or 4 adverse event that is definitely, possibly, or probably related to BMX-001 treatment during this same period.

Adverse events occurring between baseline through 2 weeks after discontinuation of radiation will be the focus of these analyses and will be summarized.

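### Protocol 13.7.1 and 13.7.2 end safety assessments at progression, while 14.1 and Table 4 require them to at least 30 days after last treatment

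*Protocol*

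**What the plan says.** **Rules that stop collection.** Protocol section 13.7.1, under disease progression, keeps four cognitive instruments (HVLT-R, COWA, TMT, BAC App) and adds: "All other assessments will stop at the point of" progression. Section 13.7.2, on patients withdrawn for toxicity or progression, says: "Study visits will cease, however data collection for survival should continue at a minimum of three month intervals". It also says that these patients "will be followed for as long as they are receiving treatment for their HGG at the clinical center", without naming the data to be collected.

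**Rules that require collection.** Section 14.1 sets the AE window: "From the time the subject signs the informed consent form through 30 days after completion of the final BMX-001 treatment" in Arm A, and 30 days after the last chemo/RT in Arm B. Within it, "all AEs must be recorded in the subject medical record and adverse events case report form". Table 4 lists toxicity assessment and CBC among the scheduled evaluations, and footnote i reads: "Toxicity assessment will continue to be obtained at every SOC clinic visit during the Adjuvant Phase for a minimum of 30 days after last BMX-001"; where no BMX-001 is given, the 30 days run from the last chemo/RT. Neither place makes an exception for progression.

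**Analysis.** SAP section 11 reports that AE collection stopped 30 days after chemoradiation with or without BMX-001, and mentions no earlier stop. For the grade 3-4 AE endpoints, SAP section 11.1 says: "Adverse events occurring between baseline through 2 weeks after discontinuation of radiation will be the focus of these analyses". The thrombocytopenia endpoints (protocol 16.5.2.2, SAP 10.1) close at the same time. Weekly CBCs run from week 2 to week 8 (Table 4 footnote d).

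**The concern.** A site that follows 13.7.1 literally stops toxicity assessment and blood counts on the day progression is called. A site that follows 14.1 continues. No passage says which prevails, so safety follow-up may differ between sites, and the SAP assumes a complete window that some patients may not have.

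Two things are at stake. First, AEs and SAEs soon after dosing may go unrecorded. Second, for patients who progress early enough, the AE and platelet endpoints rest on shortened observation. The stopping event is itself an outcome that treatment may affect, and the trial is open-label, so the loss need not be equal between arms.

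**Working it through.** **1. Windows, in weeks from the start of RT.** Inputs: RT lasts 6 weeks; BMX-001 runs to week 8, with missed doses made up at the end and a longest interruption of 3 weeks (9.1.5); post-RT MRI comes 2 to 4 weeks after RT (13.8.4) and is the reference scan (Appendix A); later scans are about every 8 weeks, taken here with the +/- 2 weeks of Table 4 footnote b; confirmation needs a second scan at least 4 weeks later (13.8.4).

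| Event | Arithmetic | Week |
|---|---|---|
| Grade 3-4 AE and thrombocytopenia endpoints close | 6 + 2 | 8 |
| AE window closes, Arm B | 6 + 30/7 | 10.3 |
| AE window closes, Arm A, dosing on time | 8 + 30/7 | 12.3 |
| AE window closes, Arm A, 3 weeks of make-up doses | 11 + 30/7 | 15.3 |
| Post-RT MRI | 6 + 2 to 6 + 4 | 8 to 10 |
| Next scheduled scan | 8 + 6 to 10 + 10 | 14 to 20 |
| Earliest confirmed radiographic PD | 14 + 4 | 18 |

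**2. Who is caught.** On scheduled scans read against the post-RT MRI, confirmed radiographic PD (week 18 or later) falls after every AE window. If the screening scan were the reference, preliminary PD could be called at weeks 8 to 10 and confirmed from week 12, just inside the Arm A window. Section 13.7.1 does not say whether its stopping point is preliminary or confirmed PD.

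Neurological progression needs no second scan. Item 3 of the progression criteria (13.8.4) admits it, and the response table in Appendix A maps worse neurological status with stable or increasing steroids to confirmed PD whatever the target lesions show. Neurological examinations are scheduled every other week in weeks 1 to 8 (Table 4 footnote c). This route can fall inside the AE window and, before week 8, inside the endpoint windows.

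**3. What is lost.**
- Progression before about week 8: weekly CBCs, both grade 3-4 AE endpoints and both platelet endpoints are cut short, and so is the later AE tail.
- Progression after about week 8 but inside the AE window: only the all-AE and SAE tables are affected.

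**4. How such patients would be counted.** The endpoints are simple proportions. The Safety population needs one dose of BMX-001 or TMZ (SAP 6), so an early progressor stays in the AE denominator. Thrombocytopenia is tabulated in ITT and Treated (SAP 19). Treated requires completed chemoradiation and, in Arm A, at least 13 BMX-001 doses, so an early progressor may be outside it. No rule covers an incomplete AE or platelet window. The only explicit rule of this kind is for radiographic response (SAP 13.2).

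**5. Illustration for the platelet endpoint.** The plan's own figure first: 80 per arm, 15% against 4%, one-tailed alpha 0.05, stated power 80%. With the arcsine formula, h = 2 asin(√0.15) − 2 asin(√0.04) = 0.393, and power = Φ(0.393 × √40 − 1.645) = 79.9%. The exact one-sided chi-square calculation gives 80.1%. The figure is reproduced.

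Now assume that a share f of patients leaves before week 8, loses a share w of its event risk, and is counted as event-free. Each rate is multiplied by 1 − f·w.
- Equal loss in both arms: power 79.5% (f = 2%, w = 0.5), 77.9% (f = 10%, w = 0.5), 73.5% (f = 15%, w = 1).
- No true effect (15% in both arms), loss in Arm A only, w = 1: one-sided type I error goes from 4.95% to 6.46%, 8.35% and 10.68% at f = 5%, 10% and 15%.

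All values of f and w are assumptions. The one-arm case is an extreme.

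**The case against.** The strongest reply is that AE duties belong to section 14, that the study-assessments section (13.8) has no AE item, and that SAP section 11 reports collection to 30 days with no earlier stop, so sites probably carried on. Section 13.7.2 also keeps patients under follow-up while they are treated at the center. This is a reasonable guess at practice, but it does not settle the text: Table 4 lists toxicity assessment and CBC as scheduled evaluations, 13.7.2 names no data beyond survival, and the SAP sentence does not address progressors.

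Several stronger readings are tempting, and the documents do not support them.
- A reader might infer that 14.1 requires platelet counts for 30 days after the last dose. It requires AE recording and sets no platelet schedule.
- A reader might infer that any progression inside the 30-day window biases the formal endpoints. Both close about week 8, so later progression cannot change them.
- A reader might infer that early progressors are counted as event-free by rule. That is only what a simple proportion does by default, and they may fall outside the Treated population.
- A reader might infer that everything except cognition stops. Survival follow-up continues.
- A reader might infer that drug toxicity would be relabeled as progression. Item 3 excludes worsening that has another cause, so recognized toxicity does not qualify. What remains is worsening whose cause is uncertain when the call is made.

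**Conclusion.** The contradiction stands: 13.7.1 and 13.7.2 cannot be reconciled with 14.1 and Table 4 footnote i for a patient called progressive inside the AE window. It concerns chiefly patients who progress on neurological worsening. Those who do so before about week 8 also have shortened endpoint data; for later ones only the all-AE and SAE tables suffer.

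The size is unknown, because neither document gives an early-progression rate. The illustration suggests that roughly equal loss in both arms costs little unless it is large, and that one-sided loss matters more, but it rests wholly on assumed rates and on the unstated event-free default. The week counts assume six weeks of RT and scans on schedule. This is a minor point, worth making because the stopping rule, if followed, removes safety data that the protocol requires elsewhere.

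**What to change.** **Protocol.** Reconcile 13.7.1 and 13.7.2 with 14.1 and footnote i. For example, in both sections: *other assessments stop at progression, except AE and SAE recording to the end of the section 14.1 window, platelet counts to 2 weeks after RT, and survival follow-up.* Also state whether the stopping point is preliminary or confirmed progression.

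**SAP.** Treatment and AE collection are already described in the past tense, so rewording the protocol will not recover lost data. Add:
- a listing, by arm, of patients whose AE or platelet window was cut short by progression, with the date of the call relative to each window;
- a sensitivity analysis of the AE and platelet proportions that excludes these patients or accounts for their shorter observation. Exclusion conditions on a post-randomization outcome, so it should stay a sensitivity analysis.

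**Cost.** A sentence in each of two protocol sections, one listing and one repeat analysis. SAP section 7 already lists withdrawals by arm with reasons, and section 18 already allows sensitivity analyses in general terms. Nothing is collected beyond what 14.1 and Table 4 already schedule.
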